In addition to the above considerations, this intervention targets the role of patient facing technologies in health information sharing. The availability of both patient and provider-facing technologies to improve health information exchange is rapidly evolving. The My HealtheVet Program Office anticipates that veterans will be able to send their CCD electronically directly from the MyHealtheVet website as of Fall/Winter 2014. In addition, [name] is working with local and national initiatives to promote provider-to-provider and state-based health information exchanges where the patient is not the intermediary. Though exciting, these technical developments are not currently available so they could not be incorporated into the design of this study. However, if they do become available during the study, the team and the Executive Committee will explore whether or not it would make sense to revise study methods to include them. The main focus of the assessments within the study is not whether a specific technology is used, but whether there is accurate and timely communication. At this level of analysis, we may be able to change the specific technology used, yet still determine the impact of health information sharing on the quality and efficiency of care provided.

Sample: Sixty dual use veterans who have a non-VA provider and who are not already using My HealtheVet for health information sharing will be recruited from the Iowa City VA Health Care System. Based on earlier research that identified criteria for optimal impact of CC(15-17), participants must have at least one of the following chronic illnesses or ambulatory care sensitive conditions: diabetes, chronic obstructive pulmonary disease, hypertension, congestive heart failure, angina, asthma, coronary artery disease, arthritis, gynecologic conditions, or cancer -as determined by medical record review. We will oversample women veterans so that the final sample contains at least 20 women veterans -30% of the total sample. Eligible veterans will be sent a recruitment letter with a postage paid return postcard asking them to indicate whether they have a non-VA provider or have ever used My HealtheVet for sharing health information with providers. When contacted, the research assistant will confirm inclusion criteria and request the date of the next scheduled VA-provider and

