non-VA provider appointment. Only those with upcoming visits with both providers in the next 6 months will be recruited. In our current work, we were able to use comparable methods to find veterans who had non-VA providers and we expect similar success in this study. To complete the study procedures, participants will be required to have access to a computer with internet, phone, and printer. At the time of enrollment, veterans will also be asked to complete a release of information so we may communicate with their non-VA provider and obtain a copy of their recent visit note, problem list, and medication list.

This pilot will be a randomized controlled trial comparing the CC intervention to usual care. This will allow for more conclusive determination of the impact of the intervention. In addition, results from this pilot can be compared to Dr.[name]'s pilot study examining unidirectional sharing of health information from the VA to non-VA providers only, to determine whether there was any additional benefit to bi-directional information sharing, the inclusion of the Co-Management Toolkit, and discussion of provider roles.

The study statistician will develop a computer program to implement randomization grouped in blocks to ensure equal distribution in study arms by age, gender, and race. The study coordinator will maintain randomization assignments in sealed envelopes to ensure that randomization and recruitment of specific patients is not influenced by future assignments. Veterans and providers in the usual care condition will complete all the same assessments, but will otherwise receive no aspects of the intervention.

Intervention Arm:

Veteran Intake Interview: In the intake interview, conducted by phone, veterans will be asked to confirm their medical conditions and list all their providers, including pharmacies, provide provider contact information, and to specify what roles and responsibilities are held by these providers (initial draft of form can be found in Appendix C). Veterans will also provide the dates of upcoming VA and non-VA provider visits. The results of the interview will be summarized. Veterans will also complete the Patient Perceptions of Integrated Care Survey(18, 19) with instructions to rate their experience in the past year. This initial assessment will serve as the baseline measure for patients' perceptions of CC.

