Hypothesis 1: Patients in the intervention arm will have greater increase in the Perceptions of Integrated Care Survey score from baseline to the two provider visits when compared with usual care. This hypothesis will involve three dependent sample t-tests, assuming that Patient Perceptions of Integrated Care are distributed normally (if not normally distributed, analyses will use a Wilcoxon rank sum test). Specifically, we will examine differences between intervention and usual care patients with respect to the within-patient change between baseline perceptions and 1) perceptions after the first subsequent visit with a VA provider, 2) perceptions after the first subsequent visit with a non-VA provider, and 3) perceptions after subsequent VA and

non-VA provider visits averaged. Sub-analyses looking for differences between demographic groups based on age and gender will also be conducted.

Hypothesis 2: Providers in the interventional arm will have higher scores on the Relational Coordination Survey as compared to that of providers in usual care. The Relational Coordination survey will be completed by providers at each patient's first VA visit and first non-VA visit subsequent to baseline. Assuming coordination perceptions are normally distributed, analysis will use independent sample t-tests to evaluate differences in relational coordination perceptions between providers caring for patients in the treatment and usual care groups (alternatively, the Wilcoxon test may be used for non-normal measures). Differences in perceptions between usual care and treatment groups will be evaluated separately for VA providers and non-VA providers. These analyses assume that no two patient participants share a provider. If this assumption is not met, analyses will be adjusted to account for clustering within physician.

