Hypothesis 4: Medical duplication will be lower for patients in the intervention arm than usual care. Prior research has quantified therapeutic and laboratory duplication, yet these are clearly difficult constructs to operationalize(10, 21-23). Therapeutic duplication will be defined as concurrent use of more than one medication from the same therapeutic class, based on modified VA classes, according to the method published by Fitzgerald et al. (24) and more recently adapted by Chrischilles et al.(10). For laboratory duplication, we will identify all orders for labs occurring within the 6 months prior to the non-VA provider visit. For sensitivity analysis, we will compare different intervals, e.g., 14 days, 30 days, 60 days. Since there are multiple indications for laboratory referrals, we will collect temporally associated diagnoses. Each patient will be assigned a dichotomous indicator for whether they received therapeutic duplication and/or laboratory duplication during their non-VA provider visit.

To validate these metrics, all instances of identified duplication plus a random sample of visits where no apparent duplication occurred will be reviewed by [name], a clinical pharmacist, and [name], head of the ICVAHCS pathology department. Both are current collaborators on [name] HSR&D and ORH study. Drs. [name] and [name] will be blind to whether or not the visit met criteria for treatment or diagnostic redundancy and they will also be blind to the treatment arm of the patient whose visit is being reviewed. Their clinical assessment of presence of duplication will be used to validate the metric. If agreement is poor between these two raters and the criteria described above (Kappa > 0.80), the investigative team will meet to determine the source of the discrepancy and how to remedy it. Each patient will be assigned a dichotomous indicator for whether they received either therapeutic or laboratory duplication during their non-VA provider visit. Differences in the occurrence of medical duplication between usual care and intervention groups will be examined using the Chi-square test.

REFERENCES

1. 2011 Survey of Veteran Enrollees' Health and Reliance upon VA. . 2011.

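### Randomisation is blocked on age, gender and race, but no planned between-arm test accounts for them; if they are prognostic, precision is lost and the SD carried forward is too large

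*Combined protocol and SAP*

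**What the plan says.** The randomised-design paragraph, just before the Intervention Arm heading, says the statistician's program will "implement randomization grouped in blocks to ensure equal distribution in study arms by age, gender, and race". It gives no block size, age cut-points or race categories. The Sample paragraph sets the size at "Sixty dual use veterans who have a non-VA provider" and adds: "We will oversample women veterans so that the final sample contains at least 20 women veterans".

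The analyses are in the section on outcome assessments and quantitative analysis:

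- **Hypothesis 1** (integrated care survey): "This hypothesis will involve three dependent sample t-tests". The text goes on to describe these as comparing the arms on within-patient change. Wilcoxon is the fallback. It adds: "Sub-analyses looking for differences between demographic groups based on age and gender will also be conducted".
- **Hypothesis 2** (relational coordination): "analysis will use independent sample t-tests to evaluate differences in relational coordination perceptions", with Wilcoxon as the fallback. If patients share a provider, "If this assumption is not met, analyses will be adjusted to account for clustering within physician".
- **Hypothesis 3** (medication concordance): chi-square on categories, or a t-test or Wilcoxon test, depending on the distribution.
- **Hypothesis 4** (duplication): differences between the arms "will be examined using the Chi-square test".

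The same section says that the pilot's analyses are meant to supply an effect size and a variability figure for sizing a later study. No alpha, power or target difference is stated.

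**The concern.** Blocking on a factor makes the arms alike on it, so its contribution to the outcome largely cancels from the difference between arms. An unadjusted test still counts that contribution in the within-arm variance, and hence in the standard error. When the factor is prognostic, the standard error describes a less balanced design than the one that was run. Intervals are then too wide, the nominal 5% test rejects less often than 5% under the null, and the precision bought by blocking is not used.

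In this pilot the larger consequence may be the SD. A later trial that adjusts for the same factors should be sized on the residual SD. If the pilot reports only the unadjusted SD, the later trial is sized on too large a figure.

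**Working it through.** **Inputs from the documents.** 60 veterans, at least 20 of them women; blocking on age, gender and race; unadjusted tests. There is no power figure in the plan to reproduce.

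**Assumptions.** 1:1 allocation (30 per arm), two-sided 5%, total outcome SD of 1 before any treatment effect, no dropout, permuted blocks of 4 within gender × age (two groups) × race (10% in the smaller group), that is, 8 strata. R² is the assumed share of outcome variance explained by the blocking factors.

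**Large-sample formulas, with perfect balance.**

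- Unadjusted SE ÷ adjusted SE = 1/√(1−R²). At R² = 0.20: 1/√0.80 = 1.12.
- True type I error of the nominal 5% unadjusted test = 2·[1−Φ(1.96/√(1−R²))]. At R² = 0.20: 1.96/0.894 = 2.19, giving 2.8%.
- Sample-size multiplier if an adjusted later trial is sized on the unadjusted SD = 1/(1−R²). At R² = 0.20: 1/0.80 = 1.25.

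**Simulation, continuous outcome.** The adjusted model is linear in arm, age, gender and race. The power columns use a 0.6 SD effect, with 6,000 trials per row and age and gender carrying the R². The simulated type I columns come from a separate set of 8,000 trials per row in which all three factors share the R² equally.

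| R² | SE ratio (formula) | Type I, unadjusted (formula) | Type I simulated: unadjusted / adjusted | Power simulated: unadjusted / adjusted | Later-trial multiplier |
|---|---|---|---|---|---|
| 0 | 1.00 | 5.0% | 5.6% / 5.6% | 61.3% / 60.5% | 1.00 |
| 0.02 | 1.01 | 4.8% | 5.1% / 5.3% | 63.3% / 63.2% | 1.02 |
| 0.05 | 1.03 | 4.4% | 4.4% / 4.8% | 62.2% / 63.5% | 1.05 |
| 0.10 | 1.05 | 3.9% | 4.1% / 5.2% | 62.5% / 65.9% | 1.11 |
| 0.20 | 1.12 | 2.8% | 3.4% / 5.0% | 63.2% / 71.3% | 1.25 |
| 0.30 | 1.20 | 1.9% | 2.7% / 5.1% | 64.7% / 77.6% | 1.43 |

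Monte Carlo standard error is about √(0.63×0.37/6000) = 0.6 points for each power figure and √(0.05×0.95/8000) = 0.2 points for each type I figure. A repeat with fresh random numbers gave the same pattern.

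The simulated conservatism is milder than the formula's at the larger R² because many blocks are incomplete. With 60 patients in 8 cells the average is 7.5 per cell, and the four cells of the smaller race group share about 6 patients. In the 8,000-trial set, the mean t-test SE against the actual SD of the estimate was 0.258 against 0.250 at R² = 0.10 (3% too large) and 0.258 against 0.230 at R² = 0.30 (12% too large).

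**Binary outcome (Hypothesis 4).** The figures above do not carry over. A rough check compared a gender-stratified Mantel-Haenszel test with the ordinary chi-square at n = 60, with an assumed absolute risk reduction of 0.30. With duplication in 50% of women and 35% of men, power was 81.4% against 80.7%. With 55% and 35% it was 79.7% against 78.1%. The gain is 1 to 2 points even with a 15 to 20 point gap between the sexes.

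**The case against.** The strongest reply is that the effect is conditional and the documents do not establish the condition. No passage reports that age, gender or race predicts any of the four outcomes. Hypothesis 1 analyses change, which may remove part of any stable demographic effect. Hypothesis 2 is the provider's own rating, and nothing suggests that a patient's demographics explain much of it. Oversampling women raises gender's share of variance only if gender matters. At R² of 0.05 or below the difference is negligible. All of this stands. A reader might infer that the standard errors are too large and that power is being lost; the documents support only the conditional statement.

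A second reply is that the pilot has no planned power to lose. That is correct, and the power figures serve only to give a scale. But the stated purpose is to estimate an effect size and its variability, and the choice of SD bears directly on that.

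A third is that the block scheme used here is assumed. That also stands: a coarser or looser scheme would give less balance and less conservatism.

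Against these, the investigators chose the three factors as worth balancing and planned sub-analyses by two of them. That makes some prognostic value plausible, though not shown. The age and gender sub-analyses and the clustering adjustment do not answer the point, because neither adjusts the arm comparison for the blocking factors.

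**Conclusion.** The point holds in conditional form. The plan blocks on three factors and leaves them out of every between-arm test. If they are prognostic, the unadjusted analysis is conservative and less precise than the design allows, and its SD is too large for sizing an adjusted later trial. Under the assumed scheme and a 0.6 SD effect, the power gain for continuous outcomes is about 1 point or less at R² of 0.05 or below, about 3 at 0.10 and about 8 at 0.20. A later adjusted trial sized on the unadjusted SD would be about 5%, 11% and 25% too large at R² of 0.05, 0.10 and 0.20. If the factors are not prognostic, almost nothing changes. For Hypothesis 4 any gain is likely small.

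A reader might also infer a threat to validity or an excess of false positives. Neither follows: omitting the factors does not bias the estimated difference in means or proportions, and the error in the test is on the conservative side. This is an inexpensive improvement to efficiency and reporting.

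**What to change.** Prespecify in the analysis section:

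- **Continuous outcomes (Hypotheses 1 to 3):** compare arms with a linear model containing arm and the randomisation factors (age, gender, race) as additive main effects. For Hypothesis 2, keep the planned adjustment for clustering within physician in the same model.
- **Rank or categorical fallback:** use a version stratified by gender, for example van Elteren in place of Wilcoxon and Mantel-Haenszel in place of chi-square.
- **Hypothesis 4:** use a Mantel-Haenszel risk difference stratified by gender. This avoids a multi-term logistic model, which could be unstable in 60 patients if duplication is rare.
- **Sensitivity and reporting:** keep the present unadjusted tests as sensitivity analyses, and report both the adjusted residual SD and the unadjusted SD so that the later power calculation can use the one matching its own analysis.
- **Scheme:** state the block size, age cut-points and race categories, so that the model can be checked against the allocation.

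The cost is a few sentences and no new data, since the factors are already needed for randomisation. With binary race the model uses three more degrees of freedom (60 − 5 = 55 residual, against 60 − 2 = 58 for the t-test); more race categories would use more. If the factors turn out not to matter, the power loss is negligible (60.5% against 61.3% in the R² = 0 row).

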The Patient Perception of Integrated Care Survey (Appendix D) is a 33-item measure assessing perceived coordination within the care team, across care teams, between care teams and community resources, continuity, patient centeredness and shared responsibility. It has demonstrated internal consistency, discriminant validity, and goodness-of-fit.

Upon completion of the intake interview, study staff will send the veteran the training materials and link to online training videos that teach the veteran to use My HealtheVet to generate a CCD, share with their non-VA provider, and to compile information from non-VA providers that can be shared with VA providers through secure messaging. If the non-VA provider supports an online patient portal (e.g. Epic's My Chart), the staff will assist the veteran in using that tool if the veteran is amenable. A research assistant will contact the participant by phone to determine if they are having difficulties with the program and to provide any further assistance needed to bring success. In-person training and assistance will be offered when needed. In [name] current study, veterans have rarely needed assistance beyond the training materials provided. It appears that once veterans are made aware of the Blue Button Feature, the value of the feature in CC, and receive some guidance about how to go about generating a CCD, they can be fairly independent progressing through the whole process. More of a challenge has been finding veterans with scheduled visits within the next 6 months, though the original study did not target veterans with specific chronic or ambulatory care sensitive conditions. We expect that these patients will have more regular visits to manage their illness.

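### The plan does not say that the baseline survey for Hypothesis 1 is completed before allocation is disclosed, and its written order suggests that it is not

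*Combined protocol and SAP*

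**What the plan says.** All references are to the Combined protocol and SAP.

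- **Randomisation.** The text just before the Intervention Arm heading describes "randomization grouped in blocks to ensure equal distribution in study arms by age, gender, and race". On concealment it says: "The study coordinator will maintain randomization assignments in sealed envelopes to ensure that randomization and recruitment of specific patients is not influenced by future assignments". It does not say when an envelope is opened.
- **Usual care.** The same paragraph ends: "Veterans and providers in the usual care condition will complete all the same assessments, but will otherwise receive no aspects of the intervention".
- **Intake interview.** This is the first item under Intervention Arm: "In the intake interview, conducted by phone, veterans will be asked to confirm their medical conditions". Veterans then list their providers and state what each provider is responsible for. They also complete the survey, "with instructions to rate their experience in the past year". The plan adds: "This initial assessment will serve as the baseline measure for patients' perceptions of CC".
- **What follows.** "Upon completion of the intake interview, study staff will send the veteran the training materials".
- **Status of the interview.** The Overview of Pilot Intervention lists the care-team interview among the new components of the intervention. The secure-messaging text under Intervention Arm has the interview decide what the veteran will send to the VA team.
- **Use of the baseline.** Hypothesis 1 compares the arms on within-patient change from this baseline to the post-VA score, the post-non-VA score and their average. Table 2 shows one baseline survey without separating the arms.

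**The concern.** The survey is a subjective rating of how well care is coordinated. A veteran who has just learned that he or she will, or will not, receive help with coordination may rate the past year differently. So may a veteran who has just been asked which provider is responsible for what. If either influence acts in one arm and not the other, the baselines differ for a reason unrelated to care received, and subtracting the baseline carries that difference into the treatment contrast with the opposite sign.

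All three Hypothesis 1 comparisons share this baseline, so all three would be affected. The pilot's stated purpose is to supply an effect size and variability for a later power calculation, so a biased contrast would carry over into the sizing of the next study.

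**Working it through.** **Step 1: is the sequence stated?** The plan gives no alpha, power, SD or effect size for this outcome, so there is no figure to reproduce. The question is the order of events.

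- Pointing to a baseline taken with the arm known: randomisation is described first; the interview then opens the Intervention Arm text; the Overview counts it as an intervention component; and it plans the content of secure messages, which only intervention veterans are trained to send.
- Compatible with a baseline taken before disclosure: the Overview places the interview once dual users have been identified and does not mention randomisation, and training materials go out only after the interview. Enrolment, interview, envelope, training would fit both.
- Blinding: the only blinding described is that of the two reviewers of duplication under Hypothesis 4. None is described for veterans or for whoever conducts the intake call.

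The sequence is therefore not stated, and the written order leans towards disclosure first.

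**Step 2: what would a shift do?** Suppose intervention veterans rate baseline lower by *d* (in SDs of the survey score) because of what they know or were asked, and a fraction *c* of that shift persists to follow-up. The bias in the change contrast is then

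bias = *d* − *c·d* = (1 − *c*)·*d*.

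With *c* = 0 the whole shift enters. With *c* = 1 it cancels. If baseline is shifted upwards, the sign reverses.

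**Step 3: illustration with *c* = 0.** Inputs:

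- 60 veterans in total (Sample section); 30 per arm assumes 1:1, as no ratio is stated.
- Assumed: two-sided 0.05, equal SDs at both times, baseline-to-follow-up correlation ρ of 0.3 to 0.7, and *d* of 0.1 or 0.2.
- Assumed: a two-sample comparison of change scores, which is what Hypothesis 1 describes although it names dependent-sample tests.

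Formulas, in units of the score SD:

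- SD of change = √(2(1 − ρ))
- SE of the contrast = SD of change × √(2/30)
- false-positive rate = Φ(−1.96 + *d*/SE) + Φ(−1.96 − *d*/SE)

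| ρ | SD of change | SE | rate, *d* = 0.1 | rate, *d* = 0.2 |
|---|---|---|---|---|
| 0.3 | 1.183 | 0.306 | 0.062 | 0.100 |
| 0.5 | 1.000 | 0.258 | 0.067 | 0.121 |
| 0.7 | 0.775 | 0.200 | 0.079 | 0.170 |

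For example, at ρ = 0.7 and *d* = 0.2, *d*/SE = 0.2/0.200 = 1.0, so the rate is Φ(−0.96) + Φ(−2.96) = 0.170. A noncentral *t* with 58 df gives nearly the same ranges: 6.2% to 7.8% for 0.1 SD and 9.9% to 16.6% for 0.2 SD.

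**Step 4: how far the result depends on carry-over.** If half of a 0.2 SD shift persists, the bias is (1 − 0.5) × 0.2 = 0.1 SD and the *d* = 0.1 column applies. If all of it persists, the rate is 0.05.

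**Step 5: would covariate adjustment remove it?** Not in the no-carry-over case. With baseline as a covariate the bias is ρ·*d*. For *d* = 0.2 that is 0.06 to 0.14 SD, with a false-positive rate of 0.057 to 0.118: smaller, but not zero.

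**The case against.** The strongest reply is that post-allocation timing is inferred from page layout. Nothing says when an envelope is opened, and the heading is a loose guide, because no usual-care heading follows it and the text beneath runs on into procedures for both arms. This stands. A reader might infer that the baseline is certainly taken after randomisation, but the documents do not establish that.

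Other stronger readings also lack support:

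- **Usual care has no baseline.** The plan says that its veterans complete the same assessments.
- **Training contaminates the baseline.** Training follows the interview on any reading.
- **The role questions come before the survey.** The text says that veterans also complete the survey, which fixes no order within the call. If both arms answer the role questions under the same conditions, any effect is common to both and cancels.
- **Veterans are lost unevenly between allocation and baseline.** Nothing in the documents shows this.

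It is also fair to say that a false-positive rate is a secondary yardstick in a pilot meant for estimation, and that a rating shift from knowing the arm might persist to the post-visit surveys and cancel.

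What the reply does not remove is the conflict over the role interview. If usual care completes it, those veterans receive something that the Overview counts as intervention, against the statement that they receive none. If they complete only the survey, the two baselines may be collected under different conditions. The plan needs to settle this on either reading.

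**Conclusion.** The concern holds in a limited form. The plan does not secure the baseline survey against knowledge of allocation, and followed in its written order it would collect a subjective baseline with the arm known. This is more than a missing detail, because the order of one step decides whether the Hypothesis 1 contrasts and the pilot effect size are exposed to the bias.

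The size and direction of any real shift are unknown. The range of about 6% to 17% against a nominal 5% illustrates assumed shifts of 0.1 to 0.2 SD, 30 per arm, correlations of 0.3 to 0.7 and no carry-over. It does not estimate what this trial would show. With partial carry-over the bias is smaller, and with full carry-over it is nil. For the effect-size estimate, the matching statement is a bias of up to 0.1 to 0.2 SD under the same assumptions.

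**What to change.** 1. State that in both arms the Patient Perceptions of Integrated Care Survey is completed at enrolment, before the envelope is opened and before any provider-role questions.
2. Move the survey text out of Intervention Arm into a section covering all participants before randomisation.
3. Keep the provider-role interview after allocation as an intervention component. Alternatively, say explicitly that usual care completes it too, and reconcile that with the statement that usual care receives no aspects of the intervention.

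With the survey completed before disclosure, the differential shift from knowing the arm is zero by design and the change-score comparison keeps its nominal error rate in this respect.

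The cost is small: one step is re-ordered and a few sentences change. The plan already has an enrolment step, at which the release of information is requested, and the survey could be attached to it. The drawback is that the survey may be separated from the rest of the intake call, which could mean one more contact for some veterans.
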